## **OBJECTIVES**

The goal of this post-market study is to evaluate safety and efficacy of the AEON™ Endostapler when used in VATS or open lung resection surgery (lobectomy or wedge resection). Patients eligible will be over the age of 18 and undergoing planned lobectomy or wedge resection. The study will include 30 total consecutive patients that meet eligibility criteria. The procedures will be performed according to institutional standard-of-care and all subjects will undergo standard preoperative evaluation as well as postoperative care. Relevant data will be collected using the Case Report Form which should be filled out following each procedure by a member of the surgical or nursing team.

**Enrollment:** 80 Subjects Meeting Inclusion/Exclusion Criteria

**Investigator Masking:** None (Open Label)

**Device:** AEON™ Endostapler

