## **STUDY DESIGN**

Patients satisfying the inclusion and exclusion criteria will be consecutively evaluated. Enrollment will be contingent on meeting these criteria, and the use of the AEON™ Endostapler.

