### **Primary Outcome Measure:**

- Incidence of reported device-related adverse events through 30-day post-operative evaluation period

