## **METHODS**

The study will include 80 total procedures on consecutive patients which will be performed by either [name] or [name] using the AEON™ Endostapler.

All patients will undergo the standard preoperative evaluation pathway.

On the day of surgery, the surgeon will elect to use the AEON™ Endoscopic Stapler Reloads. The surgeon should read and follow the Instructions for Use and use their own clinical judgement when determining the appropriate products to use. If the reloads are used, and it is clinically appropriate, reloads from other manufacturers should not be used for that case. However, in the event of unavailability of a clinically appropriate AEON™ Endoscopic Stapler Reload, a similar reload from another manufacturer is

allowed. At the end of each case, a member of the surgical or nursing team will fill out the Case Report Form.

All typical post-operative care will continue, including during the immediate post-operative period prior to hospital discharge. Regularly scheduled follow up appointments will be scheduled based on the preference and practice pattern of the surgeon and institution.

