**Statistical Analysis Plan:**

This is an open-label study. The number of subjects was chosen based on feasibility and is considered sufficient to meet the study objectives. Detailed methodology for summary and statistical analyses of the data collected in this study will be documented in the Clinical Study Report. Mean and standard deviation will be used for continuous data.

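### The protocol states two contradictory total sample sizes, 30 and 80, and the SAP does not say which one governs

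*Combined protocol and SAP*

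**What the plan says.** The combined protocol and SAP refers to the size of the study in four places:

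- **Objectives, narrative paragraph:** "The study will include 30 total consecutive patients that meet eligibility criteria".
- **Objectives, Enrollment line, a few lines later:** "80 Subjects Meeting Inclusion/Exclusion Criteria".
- **Methods, opening sentence:** "The study will include 80 total procedures on consecutive patients".
- **Statistical Analysis Plan:** "The number of subjects was chosen based on feasibility and is considered sufficient to meet the study objectives". No figure is attached.

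The number applies to a single binary primary outcome: "Incidence of reported device-related adverse events through 30-day post-operative evaluation period". Study Design adds the entry rule: "Enrollment will be contingent on meeting these criteria, and the use of the AEON™ Endostapler". The SAP describes the study as open-label and names one summary method: "Mean and standard deviation will be used for continuous data". It gives no hypothesis, performance goal, interval method or precision target, and it leaves detailed methodology to the Clinical Study Report.

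**The concern.** The two figures cannot both be the study total. No other enrolment endpoint is given: there is no closing date, interim rule or event-driven target. The SAP's claim of sufficiency therefore rests on a number that it does not state and that the protocol gives in two ways.

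Two things are at stake. First, the primary outcome is an incidence, so the total fixes its denominator and largely determines how strong a safety statement the result can support. A clean result in 30 patients says much less than a clean result in 80.

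Second, outcomes are visible as they accrue. Ending at 30 could be defended from the Objectives paragraph, and continuing to 80 from the Enrollment line and Methods. The document does not rule out making that choice after events have been seen. No intent is suggested, but a reader of the final report could not tell whether the study completed, stopped early or overran.

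**Working it through.** **Inputs.** The totals 30 and 80 come from Objectives and Methods, and the binary outcome from Primary Outcome Measure. The documents give no alpha, power, expected rate, margin or dropout allowance, so neither total can be reproduced from a calculation. The 95% level and the true event rates below are assumptions. Events are taken as independent with a constant rate.

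**Step 1. Can the figures be reconciled?** The ratio is 80/30 = 2.67.

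- *Subset or stage.* The 30 and the 80 in Methods are each described as a total. Nothing presents 30 as an interim, evaluable or per-site number.
- *Per-surgeon quota.* Methods refers to two surgeons. Then 2 × 30 = 60, not 80, and 80/2 = 40, not 30.
- *Dropout.* 30/(1 − 0.10) = 33.3, rounded up to 34. 30/(1 − 0.20) = 37.5, rounded up to 38. Reaching 80 would need a loss of 1 − 30/80 = 62.5%.
- *Procedures versus patients.* The Enrollment line counts 80 in subjects, so several procedures per patient cannot explain the gap. Prior lung surgery is also an exclusion, so a patient should not re-enter.

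None of these readings works.

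**Step 2. Precision with no events.** The exact (Clopper-Pearson) upper limit for 0/n is 1 − 0.025^(1/n) two-sided and 1 − 0.05^(1/n) one-sided.

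- n = 30: 1 − 0.025^(1/30) = 0.1157; 1 − 0.05^(1/30) = 0.0950.
- n = 80: 1 − 0.025^(1/80) = 0.0451; 1 − 0.05^(1/80) = 0.0368.

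**Step 3. Precision with some events.** Exact two-sided 95% intervals:

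| Observed | n = 30 | n = 80 |
|---|---|---|
| 0 events | 0 to 11.6% | 0 to 4.5% |
| 1 event | 0.1 to 17.2% | 0.03 to 6.8% |
| 10% (3/30 or 8/80) | 2.1 to 26.5% | 4.4 to 18.8% |

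**Step 4. Chance of seeing no event.** P(0) = (1 − p)^n. The last column, P(0 at 30) − P(0 at 80), is the chance that the study is event-free at 30 patients but has at least one event by 80.

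| Assumed true rate p | P(0), n = 30 | P(0), n = 80 | Difference |
|---|---|---|---|
| 1% | 0.740 | 0.448 | 0.292 |
| 2% | 0.545 | 0.199 | 0.346 |
| 5% | 0.215 | 0.017 | 0.198 |

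Over these rates, the choice of stopping point alone would decide between reporting no events and reporting at least one in roughly 20% to 35% of studies.

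**The case against.** The strongest reply is that this is leftover text. The figure 80 appears in the labelled Enrollment line and again in Methods, while 30 appears once, in narrative. On that reading the study has a working total of 80 and one number needs editing. This is probably right, and it is why 80 is the default in the fix. But nothing in the document says which figure governs, and the SAP, where the matter could have been settled, gives no number. The accurate word is contradictory: two totals are given, not none.

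Four further points limit the claim:

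- Neither stop satisfies the whole document. Stopping at 30 conflicts with the Enrollment line and Methods, and stopping at 80 conflicts with the Objectives paragraph. What stands is that either could be defended by selective citation.
- No interim look or outcome-dependent stop is described, and with no hypothesis test there is no stated error rate to inflate. Selective stopping is an unclosed possibility. It could still distort a descriptive incidence.
- Planned precision would remain unstated even with one total, because the SAP names no interval method or confidence level for an incidence.
- The unit also varies among patients, subjects and procedures, so changing only the number would leave the denominator loosely worded.

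The modest, feasibility-based, post-market design lowers the stakes compared with a powered trial. It does not make a 2.67-fold conflict in the only enrolment target acceptable.

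**Conclusion.** The concern holds and must be fixed. The protocol gives 30 and 80 as whole-study totals, and no plausible reading reconciles them. Parts of the document were not available to us, but nothing in them could make the Objectives section agree with itself.

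In size, the upper limit on the event rate after a clean result is about two and a half times as high at 30 as at 80 (11.6/4.5 = 2.6). These figures rest on an assumed 95% level and exact binomial limits; the no-event probabilities also rest on assumed true rates of 1% to 5%. The contradiction itself rests on the text alone.

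**What to change.** 1. The sponsor confirms the intended total. Unless it confirms 30, change the figure in the Objectives paragraph to 80, to agree with the Enrollment line and Methods. If 30 is intended, correct those two places instead.
2. Use one unit, such as enrolled patients, in Objectives, Methods and the SAP.
3. Name the total in the SAP's sample-size sentence and give the precision it provides. For example, with no events the exact two-sided 95% upper limit is 4.5% at 80 or 11.6% at 30. This also supplies the missing interval method.
4. Date the correction and record how many patients had been enrolled by then, so that a reader can see whether the total was settled before or after outcomes were known.

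**Cost:** one corrected number, an aligned unit and a sentence or two in the SAP. No extra patients are needed if 80 is the working figure. If 30 is intended, the cost is accepting and stating the wider interval.

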## BACKGROUND

The AEON™ Endostapler is comprised of a stapler handle and reloads. The handle may accept multiple reloads of single fire cartridges. The AEON™ Endostapler devices are CE certified per Certificate No. G1 003029 0001 Rev. 00. The AEON™ Endostapler devices were cleared by the United States Food and Drug Administration (FDA) under the 510(k) process. Pertinent applications numbers are K171589 and K173443.

The AEON™ Endostapler has previously been proven as safe and effective for bariatric surgery as presented by Cleveland Clinic at SAGES 2019. The AEON™ Endostapler also has been evaluated for superior hemostasis against the Ethicon stapler with research led by [name], as referenced inclinicaltrials.gov:

<https://clinicaltrials.gov/ct2/show/NCT04149925?term=AEON+or+%27Lexington+medical%27&draw=2&rank=1>.

This study aims to demonstrate safety and effectiveness for thoracic surgery.

## Approved Indications for Use

The AEON™ Endostapler has applications in general, abdominal, gynecologic, pediatric and thoracic surgery for resection, transection and creation of anastomoses.

## Available AEON™ Endostapler Reloads

The following table contains the available AEON™ Endostapler Reloads as well as their specifications. The surgeon should read and follow the Instructions for Use and use their own clinical judgement when determining the appropriate products to use.

*Table 1. Available AEON™ Endostapler Reloads*

Reload Type	Cartridge Length	Product Code	Open Staple Height	Closed Staple Height	Minimum Port Size
Gray	45mm	AESR45G	2.0mm	0.75mm	12mm
Gray (Curved Tip)	45 mm	AESC45G	2.0 mm	0.75 mm	12 mm
White	45mm	AESR45T	2.5mm	1.0mm	12mm
White (Curved Tip)	45 mm	AESC45T	2.5 mm	1.0 mm	12 mm
White	60mm	AESR60T	2.5mm	1.0mm	12mm
Orange	45mm	AESR45R	3.25mm	1.5mm	12mm
Orange (Curved Tip)	45mm	AESC45R	3.25mm	1.5mm	12mm
Orange	60mm	AESR60R	3.25mm	1.5mm	12mm
Purple	45mm	AESR45P	4.0mm	1.8mm	12mm
Purple (Curved Tip)	45mm	AESC45P	4.0mm	1.8mm	12mm
Purple	60mm	AESR60P	4.0mm	1.8mm	12mm
Black	60mm	AESR60B	5.0mm	2.2mm	15mm

## **STUDY DESIGN**

Patients satisfying the inclusion and exclusion criteria will be consecutively evaluated. Enrollment will be contingent on meeting these criteria, and the use of the AEON™ Endostapler.

### **Patient Inclusion and Exclusion Criteria:**

#### **Inclusion Criteria:**

- Patients undergoing planned VATS or open lung resection surgery (lobectomy or wedge resection)

#### **Exclusion Criteria:**

- Active bacterial or fungal infection
- Prior history of VATS or open lung surgery
- Use of staple line reinforcement material (butress)
- Patients under the age of 18 on the date of the surgery
- Any female patient who is pregnant
- Scheduled concurrent surgical procedure other than lobectomy or wedge resection (central venous access - e.g., port placement, mediastinoscopy with lymph node sampling, and VATS lymphadenectomy are allowed)

### **Primary Outcome Measure:**

- Incidence of reported device-related adverse events through 30-day post-operative evaluation period

### **Secondary Outcome Measures:**

- Incidence of product malfunction during procedure

## **METHODS**

The study will include 80 total procedures on consecutive patients which will be performed by either [name] or [name] using the AEON™ Endostapler.

All patients will undergo the standard preoperative evaluation pathway.

On the day of surgery, the surgeon will elect to use the AEON™ Endoscopic Stapler Reloads. The surgeon should read and follow the Instructions for Use and use their own clinical judgement when determining the appropriate products to use. If the reloads are used, and it is clinically appropriate, reloads from other manufacturers should not be used for that case. However, in the event of unavailability of a clinically appropriate AEON™ Endoscopic Stapler Reload, a similar reload from another manufacturer is

allowed. At the end of each case, a member of the surgical or nursing team will fill out the Case Report Form.

All typical post-operative care will continue, including during the immediate post-operative period prior to hospital discharge. Regularly scheduled follow up appointments will be scheduled based on the preference and practice pattern of the surgeon and institution.

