**Appendix A – Case Report Form**

Surgery Date: \_\_\_\_\_ Surgeon: \_\_\_\_\_ Hospital: \_\_\_\_\_

Surgery Type: \_\_\_\_\_

Patient Gender: \_\_\_\_\_ Patient Age: \_\_\_\_\_

AEON Endostapler	Black 60mm	Purple 60mm	Purple 45mm	Orange 60mm	Orange 45mm	White 60mm	White 45mm	Gray 45mm
Quantity Non-Curved Tip Reloads Used								
Quantity Curved Tip Reloads Used								

Intraoperative Outcomes								
Product malfunction during stapling? (circle one)					Yes	No		
Blood transfusion due to staple line bleeding? (circle one)					Yes	No		

*If yes to any above, please specify:*

30 Day Postoperative Outcomes		
Reported device-related adverse events? (circle one)	Yes	No

*If yes to any above, please specify:*

Investigator Signature: \_\_\_\_\_

Date: \_\_\_\_\_

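### The stated time for filling out the Case Report Form is the end of the operation, yet the same form carries the 30-day primary outcome, and no visible text says when that item is completed

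*Combined protocol and SAP*

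**What the plan says.** The primary outcome is "Incidence of reported device-related adverse events through 30-day post-operative evaluation period". The secondary outcome is confined to the operation: "Incidence of product malfunction during procedure".

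Two places say when the data form is completed. METHODS is specific: "At the end of each case, a member of the surgical or nursing team will fill out the Case Report Form". OBJECTIVES is looser and refers to the "Case Report Form which should be filled out following each procedure by a member of the surgical or nursing team", with no day given.

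Appendix A shows one form with two outcome blocks. The first covers intraoperative events. The second is headed "30 Day Postoperative Outcomes" and contains the primary outcome as one Yes/No item. The form ends with one investigator signature and one date. Apart from the surgery date at the top, it has no other date field.

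On later contact with the patient, METHODS says: "Regularly scheduled follow up appointments will be scheduled based on the preference and practice pattern of the surgeon and institution". No visible text ties a contact or a record check to day 30, or says who completes the 30-day block and when.

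**The concern.** A single completion time is applied to a form whose two blocks become answerable about a month apart. The end of the operation suits the secondary outcome and the intraoperative block. It does not suit the primary outcome, whose window has only just opened.

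Device-related events during the operation would be known when the form is filled out. Those reported later could be left off, so any resulting error favours the device in a study that aims to show its safety in thoracic surgery. This item is also the only field on the form that records the primary outcome, so no other entry on it could expose or repair the omission.

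**Working it through.** No sample-size or power calculation bears on this point. The check sets the sections side by side and then works out the weight of one misrecorded patient.

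**1. What a case is.** In METHODS the paragraph containing the form instruction opens on the day of surgery and says that "reloads from other manufacturers should not be used for that case". A case is therefore the operation. The form instruction closes that paragraph, and post-operative care and follow-up come only in the next one. Wording and order both place form completion at day 0.

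**2. Timing against each outcome.**

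| Item on the form | Window | Days of the post-operative window observed at the end of the case |
|---|---|---|
| Intraoperative block (secondary outcome) | the operation | not applicable; window complete |
| 30-day block (primary outcome) | through day 30 | 0 of 30 |

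**3. Does the word *reported* in the outcome remove the problem?** Suppose the outcome counts only events that someone brings to the team's attention. A report that arrives after the operation still arrives after a form completed at its end. It is counted only if the form is reopened, and no visible text provides for that.

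**4. What the form can and cannot show afterwards.** The surgery date and the signature date together would reveal a form signed before day 30. A blank item can also be told apart from a No. But a signature after day 30 does not show that the patient's status was checked then: a No circled at the operation and a No confirmed at day 30 look the same. The item also offers no answer for a patient whose status is unknown.

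**5. Weight of one misrecorded patient.** Inputs: N = 80 patients (enrollment line in OBJECTIVES, and METHODS). Assumption: incidence is the number of patients with Yes divided by N, since the form records one Yes/No per patient. If m patients who should be Yes are recorded as No,

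change in incidence = −m / N.

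For m = 1: −1/80 = −0.0125, or −1.25 percentage points. The unit is the patient, not the event: a missed later event changes nothing for a patient already recorded as Yes. The opening text of OBJECTIVES also gives 30 patients, for which the figure would be 1/30 = 3.3 points; that conflict in sample size is a separate matter.

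**6. Total bias.** This needs m, and the documents give no event rate, no timing of events and no proportion of forms completed early. It cannot be derived.

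**The case against.** The strongest reply is that nobody would complete the form this way. Appendix A separates the two blocks, gives each its own line for details, and heads the second one with the 30-day period, which makes little sense to answer on day 0. The wording in OBJECTIVES names no day. The staff member fills out the form while the investigator signs and dates it, a layout compatible with starting at surgery and finishing later. Nothing forbids leaving the second block open. In addition, text between METHODS and the Statistical Analysis Plan was not available to this review and may state when the 30-day block is completed.

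Much of this stands. A reader might infer that the primary outcome will in fact be entered on the day of surgery, that the study has no 30-day ascertainment, or that the reported incidence will be too low. The documents support none of these. They show a stated procedure that does not fit the outcome, not how staff will act, and the unavailable text cannot be counted as absent from the plan. If that text sets a day-30 completion, what remains is loose wording in METHODS and OBJECTIVES that should be aligned with it.

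What does not stand is that the heading settles the matter. The one explicit timing instruction points to the end of the operation, and site staff should not have to infer from a form heading when the primary outcome is recorded.

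**Conclusion.** The point holds as a mismatch between the stated form timing and the primary outcome window, and it should be fixed. Confidence is high for the textual mismatch and does not extend to its consequence.

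The downward bias is conditional. It arises if the 30-day item is answered at the operation and not updated, or if a patient whose status was never checked is recorded as No. Under either condition each patient wrongly recorded as No costs 1.25 percentage points, assuming per-patient incidence and 80 patients. That is the weight of one patient, not an estimate of the problem's size.

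**What to change.** 1. **Timing.** Amend OBJECTIVES and METHODS so that the intraoperative block is completed at the end of the case, and the 30-day block is completed and separately dated at or after post-operative day 30, by existing staff from records or routine contact. State who does this. If other text in the protocol already sets the timing, align both sections with it.
2. **Form.** Give the 30-day block its own date and add a Not assessed option, so that unknown status is not recorded as No. A date of last known status is optional.
3. **Analysis.** State in the Statistical Analysis Plan that the number of patients with unknown day-30 status is reported beside the primary incidence. Best-case and worst-case bounds are optional.

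The cost is a wording change in three sections, a revised form and one record check per patient, at most 80. It is assumed that existing staff can absorb these checks; the documents do not say. The endpoint definition and the follow-up schedule stay as they are. The reported incidence may be higher than under the present wording, by an amount that cannot be stated in advance.

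### The primary outcome runs to day 30, but neither the follow-up rule nor the form shows who was observed that long, so any resulting bias lowers the event rate

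*Combined protocol and SAP*

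**What the plan says.** Under Primary Outcome Measure, the endpoint is "Incidence of reported device-related adverse events through 30-day post-operative evaluation period". The single secondary outcome, product malfunction, is confined to the operation, so only the primary outcome needs observation after surgery.

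Under METHODS, post-operative care follows usual practice: "Regularly scheduled follow up appointments will be scheduled based on the preference and practice pattern of the surgeon and institution". The available text sets no visit, call, record check or time window at or after day 30.

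The Case Report Form in Appendix A has a block headed "30 Day Postoperative Outcomes" with one item, "Reported device-related adverse events? (circle one"), answered Yes or No, plus a line for details if Yes. The form carries two dates: the surgery date and the one beside the investigator's signature. It has no date of last contact, no event date, no source of information, and no way to record that a patient was not followed to day 30.

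On timing, METHODS says "At the end of each case, a member of the surgical or nursing team will fill out the Case Report Form", and OBJECTIVES says much the same: "Relevant data will be collected using the Case Report Form which should be filled out following each procedure". The Statistical Analysis Plan gives no denominator for the incidence and no rule for incomplete follow-up. It leaves detailed methodology to the Clinical Study Report.

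**The concern.** A 30-day incidence means something only if each patient counted as event-free was observed for 30 days, or if the shortfall is known. Here visit timing may vary, the outcome counts only events that reach the study team, and the form forces a two-way answer. A patient seen for the last time at two weeks and a patient observed for the whole month would give the same record.

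Time that nobody observed can hide events but cannot create them. With every patient in the denominator, the error therefore runs towards apparent safety. The BACKGROUND section says the study is meant to demonstrate safety in thoracic surgery, and no comparator is described that would share the under-reporting. If few events occur, one that is missed matters: at 80 patients it is worth 1/80 = 1.25 percentage points, and it could turn a nonzero rate into zero.

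**Working it through.** **Inputs from the documents.** The window is 30 days (Primary Outcome Measure). The sample size is 80 (METHODS: "The study will include 80 total procedures on consecutive patients"; the Enrollment line in OBJECTIVES: "80 Subjects Meeting Inclusion/Exclusion Criteria"). OBJECTIVES also gives 30 patients, a separate conflict; 80 is used here. The sample size rests on feasibility, with no event rate, precision target or dropout rate, so there is no planned figure to reproduce.

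**Inputs that must be assumed.** Let p be the true 30-day rate, m the share of patients last seen before day 30, and s the share of those patients' events that fall after last contact and go unreported. Early-lost patients are taken to have the same risk as the others.

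**Bias in the incidence.** With all patients in the denominator:

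expected observed rate = p × (1 − m × s); expected missed events = 80 × p × m × s.

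For p = 5%:

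| m | s = 0.25 | s = 0.5 | s = 1 |
|---|---|---|---|
| 10% | 4.88% | 4.75% | 4.5% |
| 20% | 4.75% | 4.5% | 4.0% |
| 30% | 4.63% | 4.25% | 3.5% |

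- Middle case: 5% × (1 − 0.2 × 0.5) = 4.5%; missed events 80 × 0.05 × 0.2 × 0.5 = 0.4.
- Strongest case shown: 5% × (1 − 0.3 × 1) = 3.5%; missed events 80 × 0.05 × 0.3 × 1 = 1.2.

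The relative loss is m × s whatever p is: 10% in the middle case and 30% in the strongest.

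**Chance of seeing any event.** For p = 2%, the chance of at least one reported event among 80 is 1 − 0.98^80 = 80.1% with full follow-up. In the strongest case the observed rate is 2% × 0.7 = 1.4%, and the chance is 1 − 0.986^80 = 67.6%.

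**Why the denominator must be stated.** Suppose 4 events are reported and 16 of the 80 patients are last seen early with no event reported.

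- All 80 in the denominator: 4/80 = 5.0% (exact 95% interval 1.4% to 12.3%).
- The 16 dropped: 4/64 = 6.3% (1.7% to 15.2%).
- All 16 assumed to have had an event: (4 + 16)/80 = 25%.

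The form as drawn supports only the first of these, because nothing on it identifies the 16. The second is not a safe replacement. It keeps events from patients who were later lost but drops only the event-free ones, which pushes the rate up.

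**The case against.** The strongest reply is that the outcome is defined as *reported* events in a post-market study run on standard care. A No may then mean exactly that nothing was reported, and usual practice may well bring patients back around day 30. That is fair as a description of the design. It does not make the result a verified 30-day rate, because nothing in the available text requires contact to day 30 or records that it took place.

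Four stronger readings are tempting and should not be adopted.

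- *The plan counts early-lost patients as event-free.* No sentence says so. It is the default result of a Yes/No field with no missing-data rule; a blank answer or an exclusion is possible, though not planned.
- *The bias could never be found or corrected.* Hospital records might still be searched. What holds is that the study data alone would not reveal it.
- *The plan certainly has no day-30 contact.* The text between METHODS and the Statistical Analysis Plan was not available, so a follow-up provision there cannot be ruled out. The gaps in the form and in the Statistical Analysis Plan are visible regardless.
- *Confidence limits at a reduced sample size measure the harm.* With no events, the one-sided 95% upper limit, 1 − 0.05^(1/n), is 3.7% at 80 patients and 7.2% at 40. That shows lost precision, not downward bias, and it discards the partial follow-up that early-lost patients contribute.

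It may also be said that settling when the form is completed would solve this. The instruction to complete it after each operation does need reconciling with its 30-day block. But moving completion to day 30 would not by itself ensure that anyone knew the patient's status by then.

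**Conclusion.** The point holds as a limited defect that is cheap to repair. On the available text, patients last seen before day 30 with nothing reported would by default look the same in the study data as patients followed throughout. Any bias from this runs downward.

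The size cannot be established, because the documents give neither an event rate nor the share last seen early. Under the assumptions shown, the effect ranges from slight to material: a true 5% is observed as 4.88% at the mild end and 3.5% at the strong end. If patients lost early carry a higher risk than the rest, for example because they are admitted elsewhere, the bias would be larger than the formula gives. The study can proceed, but the sponsor should make this change so that its 30-day rate can be verified as one.

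**What to change.** Leave clinical visits as they are, and add the following.

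1. **Status check.** For every patient, on or after day 30, by telephone or record review, asking about admissions elsewhere. Complete the 30-day block of the form then, and reconcile the instructions in OBJECTIVES and METHODS with this.
2. **Form fields.** Date of last known status, its source, the date of each event, and a separate yes/no item for followed to day 30. Keeping that item apart from the event question means a patient with an early event who is later lost is still recorded as having the event.
3. **Primary analysis.** Count every reported event, whenever the patient was last seen. Report the incidence over all treated patients, with the number followed to day 30 beside it.
4. **Sensitivity analysis.** State in advance one that does not treat early-lost, event-free patients as No. A Kaplan-Meier estimate at day 30, censoring at last contact, uses their partial follow-up and avoids the upward bias of simply dropping them. It assumes that loss is unrelated to risk, which should be stated.

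The cost is one short call or chart check per patient and a few form fields. The sponsor also accepts that the reported rate may be less favourable or its interval wider. No extra procedure or change to care is involved.
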